The RD analysis may not be feasible due to insufficient observed Week 24 data post discontinuation of study medication. If the number of RD participants per group is at least 50% of participants who discontinue from study medication per arm, then RD will be the primary approach to impute missing data for the TP estimand. If at least one group has either less than 50% RD participants or fewer than 5 total RD participants, then RD will not be performed, and WI will become the primary analysis method. If the minimum data requirement for the RD method is met, then WI will be implemented as a sensitivity approach for the TP estimand. The WI analysis assumes participants who prematurely discontinued from the study or who have an intermittent missing Week 24 value would have a 'washout' of any potential effect of the assigned study medication.

For all analyses involving simulated data, a seed of 8835059 will be used for random number generation.

A constrained longitudinal data analysis (cLDA) model, based on Liang and Zeger [Liang, K.-Y. and Zeger, S. L. 2000], will be used for analyses addressing the TE estimand for A1C mean change from baseline and FPG mean change from baseline. Time will be treated as a categorical variable so that no restriction is imposed on the trajectory of the means over time. The cLDA model will also adjust for treatment, the age stratum, the insulin use stratum, and the interaction of time by treatment. The cLDA model assumes a common mean across treatment groups at baseline within each age and insulin use category (due to randomization) but different means between categories, and a different mean for each treatment at each of the post-baseline timepoints. In the cLDA model, the response vector consists of baseline and the values observed at each post-baseline timepoint. The treatment difference in terms of mean change from baseline to a given timepoint will be estimated and tested from this model. An unstructured covariance matrix will be used to model the correlation among repeated measurements.

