- 1) Fit a regression model as $Y_{24} = \beta_0 + \beta_1 * Y_0 + \gamma * X + \text{error}$, where Y_0 and Y_{24} are the placebo group A1C values at Baseline and Week 24, respectively, and X is a matrix for the age and insulin stratum fixed covariates.
- 2) Impute missing Week 24 A1C values for ertugliflozin using the estimated mean from the above model and standard deviation equal to the RMSE from the model.

For participants in the placebo group:

- 1) Fit models according to the intermittent missing data pattern with A1C values from the placebo group only:
 - a. For participants with only Baseline data: $Y_{24} = \beta_0 + \beta_1 * Y_0 + \gamma * X + \text{error}$
 - b. For participants with only Baseline and Week 6 data: $Y_{24} = \beta_0 + \beta_1 * Y_0 + \beta_2 * Y_6 + \gamma * X + \text{error}$
 - c. For participants with only Baseline, Week 6 and Week 12 data: $Y_{24} = \beta_0 + \beta_1 * Y_0 + \beta_2 * Y_6 + \beta_2 * Y_{12} + \gamma * X + error$
- 2) Impute missing Week 24 A1C values for placebo using one of the 3 models above based on the missing data pattern with a mean equal to the mean from the regression model and a standard deviation equal to the RMSE from the model.

Descriptive statistics will be used to summarize the A1C mean change from baseline at Week 24 for the individual ertugliflozin dose arms in the subset of participants who were rerandomized at Visit 5/Week 12. All other continuous efficacy endpoints with the exception

of the 2 key secondary endpoints associated with hypotheses H2 and H3, including the Week 12 A1C change from baseline, will be analyzed following the same cLDA method used for the A1C TE estimand under H1 (combined ertugliflozin doses vs. placebo) and will not be analyzed under the TP estimand.

Week 54

The Week 54 analyses will be based on the same FAS population used for the Week 24 analyses. The statistical models for the analyses at Week 54 will be analogous to those at Week 24, except that no between-group comparisons will be provided for **Week 54**. The efficacy endpoints will be summarized for within-group mean change from baseline with estimates and 95% CIs calculated from the analysis model.

Table 7 summarizes the analysis strategy for primary and secondary efficacy endpoints at Week 24 and at Week 54.

Table 7 Analysis Strategy for Efficacy Variables at Week 24 and at Week 54

Variable	Estimand/Approach	Statistical Method	Missing Data Approach
Primary			

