9.9 Sample Size and Power Calculations

This study will randomize approximately 165 participants using a 2:1 randomization ratio at Visit 3/Day 1/Randomization for ertugliflozin and placebo resulting in approximately 110 participants in the ertugliflozin group (combined doses) and 55 participants in the placebo group.

TP Estimand Power

The type 1 error and power (percent of 95% posterior credible intervals <0) were simulated (10,000 simulations) using the rjags and coda packages in R and the credible intervals were

computed using the HDInterval package. With an informative prior, the type 1 error will exceed 0.05. Using the adult data from 8835-007 and a weight parameter of 0.134, a sample size of 165 will provide approximately 80% power to detect a true difference of -0.6% in the mean change from baseline in A1C between ertugliflozin and placebo, given the SD=1.5% and discontinuations from study medication as of the primary timepoint are approximately 3.9%. The type 1 error and power were estimated based on the WI approach instead of the RD approach given all randomized participants have either completed on or off study medication or have discontinued from the study in Phase A.

Regarding the secondary hypotheses, the assumptions for the efficacy of the dose-optimized ertugliflozin regimen and of the 5 mg ertugliflozin dose are the same as for the pooled ertugliflozin doses. However, the power for the secondary hypotheses will be lower than that of the primary hypothesis on account of the weighting scheme. Based on simulations, the percent reduction in power is 13% of the primary hypothesis power. Thus, the estimated power for each secondary hypothesis is 70%.

TE Estimand Power

Assuming 86% of the participants will have data at Week 24 (14% with missing data due to discontinuation from study medication or censoring after initiation of rescue), 95 participants in the combined ertugliflozin arm and 47 in the placebo arm will provide at least 80% power for the primary hypothesis test assuming that the between-group difference in A1C change from baseline at Week 24 is -0.75% and using a SD of 1.5%. Assumptions of cumulative attrition rates and covariance matrix at Week 6, Week 12 and Week 24 are listed below:

- 1. The cumulative attrition rates (due to dropout and/or censoring due to discontinuation of study medication or initiation of rescue) at Week 6, Week 12, and Week 24 are 4%, 8% and 14%.
- 2. The conditional covariance matrix is

1.11	0.8	0.6

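### Washout imputation for H2 and H3: placebo model (c) prints one coefficient for both Week 6 and Week 12, and no model covers Baseline plus Week 12 without Week 6 (minor)

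*Combined protocol and SAP*

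**What the plan says.** The WI steps for H2 and H3 in Section 9.6.1 treat the two arms differently. Ertugliflozin participants are imputed from a placebo regression on baseline and strata. For placebo the instruction is: "Fit models according to the intermittent missing data pattern with A1C values from the placebo group only". Three models follow:

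- (a) "For participants with only Baseline data": Week 24 on Baseline and strata.
- (b) "For participants with only Baseline and Week 6 data": the same plus Week 6, with coefficient β2.
- (c) "c. For participants with only Baseline, Week 6 and Week 12 data": the same plus Week 6 and Week 12, where the two added terms read "\beta_2 * Y_6 + \beta_2 * Y_{12" (subscript 12). No β3 appears.

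The next step closes the list: "Impute missing Week 24 A1C values for placebo using one of the 3 models above based on the missing data pattern". The mean comes from the chosen model and the SD is its RMSE. No rule is given for any other pattern.

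WI is a sensitivity method if retrieved-dropout (RD) imputation is feasible. If at least one group falls short of the RD data requirement, "WI will become the primary analysis method". The footnote to Table 7 applies the same switch to the key secondary endpoints.

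**The concern.** These are formulas that a programmer will code, for two hypotheses that Section 9.8 tests at alpha 0.05. Two things stand in the way of coding them without interpretation.

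First, one coefficient on two visits is an equal-slope constraint. The Week 12 A1C is closer to Week 24 and would normally carry more of the prediction, so the constraint would under-use it and over-use Week 6.

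Second, the lead-in announces intermittent patterns, but all three that are listed are monotone. Given a baseline, Week 6 and Week 12 can each be present or absent, which makes four combinations. Three are listed. The fourth, Week 12 without Week 6, has no model, so the analyst would have to choose one.

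**Working it through.** **Inputs (Section 9.9).** Under TE Estimand Power, after "The conditional covariance matrix is", the matrix for Weeks 6, 12 and 24 has variances 1.11, 1.17 and 2.25. Its covariances are 0.8 (Weeks 6 and 12), 0.6 (Weeks 6 and 24) and 0.8 (Weeks 12 and 24). I assume that it is conditional on baseline. Planned placebo n is 55.

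**Does the matrix fit the plan's own figures?** √2.25 = 1.5, the stated SD. With 95 and 47 evaluable participants, SE = 1.5 × √(1/95 + 1/47) = 0.2675. Then 0.75/0.2675 − 1.96 = 0.844, which gives power of 0.80 (two-sided 0.05), as stated.

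**Model (c) with separate slopes.** Determinant = 1.11 × 1.17 − 0.8² = 0.6587.

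- Week 6: (0.6 × 1.17 − 0.8 × 0.8)/0.6587 = 0.062/0.6587 = 0.094
- Week 12: (1.11 × 0.8 − 0.8 × 0.6)/0.6587 = 0.408/0.6587 = 0.619
- Residual variance: 2.25 − (0.6 × 0.094 + 0.8 × 0.619) = 1.698, SD 1.303

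**Model (c) as printed.**

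- Common slope: (0.6 + 0.8)/(1.11 + 1.17 + 2 × 0.8) = 1.4/3.88 = 0.361
- Residual variance: 2.25 − 1.4²/3.88 = 1.745, SD 1.321

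**Difference per participant.** The SD of the difference between the two predicted means is √(1.745 − 1.698) = 0.22 A1C points. By case:

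| Deviation from expectation | Separate | Common | Difference |
|---|---|---|---|
| Week 12 +1, Week 6 at 0 | 0.619 | 0.361 | 0.26 |
| Week 12 +1, Week 6 at its expected 0.684 | 0.684 | 0.608 | 0.08 |
| Both +1 | 0.713 | 0.722 | −0.01 |

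**How far is the matrix from equal slopes?** Let x be the Week 6–Week 24 covariance, all else fixed. The slopes are equal when 1.17x − 0.64 = 0.888 − 0.8x, so x = 1.528/1.97 = 0.776. The plan's value is 0.6.

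**The unlisted pattern (Baseline and Week 12).**

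- Slope on Week 12: 0.8/1.17 = 0.684
- Residual variance: 2.25 − 0.8²/1.17 = 1.703, SD 1.305
- Under model (a) the Week 12 slope is zero and the SD is 1.50.
- A participant 1 point off at Week 12 is then imputed 0.68 away from what the Week 12 value implies. That is 0.684/55 = 0.012 on the placebo mean per such participant.

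**Effect of the repeated coefficient on the placebo mean.** At 3.9%, 0.039 × 55 = 2.1, so about 2 values. If both are shifted the same way by 0.25 to 0.5, the mean moves by 2 × 0.25/55 = 0.009 to 2 × 0.5/55 = 0.018. As a deliberately high case, the TE attrition of 14% gives 0.14 × 55 = 7.7, about 8 values, and 0.036 to 0.073. Both the counts and the shifts are assumptions.

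**How likely is WI to be used?** RD participants cannot outnumber those who stop study medication. With independent discontinuation at 3.9%, the chance of at least 5 is 6% in placebo (n = 55), 43% in ertugliflozin (n = 110) and 77% in both together. If the minimum of 5 applies per group, WI is very likely to be primary. If it applies to the total, WI is still quite possible.

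**The case against.** The strongest reply is that the repeated subscript is a typing slip. Models (a) and (b) number their coefficients in sequence, (c) only adds a visit, and nothing in the section states an equal-slope constraint. A subscript misread from the PDF cannot be excluded either. This stands: a reader might infer that the plan intends equal slopes, and the documents do not support that.

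The matrix is a planning assumption for the TE estimand, where data after rescue or discontinuation are censored. WI serves the TP estimand, which keeps those data. This also stands, so the slopes above illustrate the point and are not estimates for the WI model.

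The 0.26-point case is an extreme profile. Weeks 6 and 12 correlate at 0.8/√(1.11 × 1.17) = 0.70, and for typical profiles the two versions differ by 0.08 or less. With a fitted intercept the differences average to zero over the fitted placebo data. A reader might infer a directional bias; none is shown.

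A reader might also infer that participants with the unlisted pattern drop out of the comparison. The text does not say so. Model (a) can be computed for anyone with a baseline, so the plausible loss is the Week 12 information. Their number is unknown and may be very small: Table 13 gives Week 6 a window of Days 2 to 63, and Section 8.10.6 allows that visit at home. Section 9.9 indicates that Phase A status was already known for everyone, so the list may reflect the patterns seen, but the document does not confirm this.

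Finally, the 3.9% is discontinuation of study medication, not missing Week 24 A1C. Those who stay in the study can supply a Week 24 value.

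What remains is that the formula as printed is not the one presumably meant, and that one of the four possible patterns has no rule.

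**Conclusion.** The point holds as a minor correction. Placebo model (c) in the WI steps for H2 and H3 carries the same coefficient on Week 6 and Week 12, and the closed list of three patterns omits Baseline plus Week 12. Under the only covariance matrix in the plan, assumed conditional on baseline, the literal formula is mis-specified, but the residual SD rises by only 1.4% (1.321/1.303).

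The expected movement of the placebo mean is one or two hundredths of an A1C point, against a planned difference of −0.6. Even the high case stays below a tenth of a point. No stated power, sample size or decision rule changes. The case for correcting it is that a confirmatory imputation should be executable as written, not that the result is in danger.

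A reader might extend this to the primary hypothesis. The documents do not support that: the WI steps for H1 are not visible in the text available, so whether they use the same formula is unknown.

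**What to change.** First check the subscript in the source PDF. If β2 is indeed printed twice, write model (c) as Y24 = β0 + β1·Y0 + β2·Y6 + β3·Y12 + γ·X + error.

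Then add pattern (d) for participants with only Baseline and Week 12 data: Y24 = β0 + β1·Y0 + β2·Y12 + γ·X + error. The four patterns are then complete for anyone with a baseline value.

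Make the same correction for H1 only if its WI steps use this formula.

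The cost is one subscript and one added line, with no effect on design or data collection. The opening of Section 9 requires a protocol amendment for changes to the statistical methods of key secondary hypotheses before unblinding. The added pattern probably falls under that rule and should be settled before then.

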9.6.2 Statistical Methods for Safety Analyses

Safety and tolerability will be assessed by clinical review of all relevant parameters including AEs, laboratory tests, and vital signs measurements. Safety analyses will be conducted across Week 0 to Week 54 (Phase A+B) with selected analyses also done across Week 0 to

[†] The primary analysis for the TP estimand will use RD to impute missing data if RD is feasible. If RD is not feasible, WI will be used.

Week 24 (Phase A). For safety and tolerability analyses, the pooled ertugliflozin group (5 mg and 15 mg) will be compared with the placebo group.

Participants will be included in the treatment group corresponding to the study treatment they actually received for the analysis of safety data using the APaT population. This will be the treatment group to which they are randomized, except for any participants who take incorrect study treatment for the entire treatment period. Such participants will be included in the treatment group corresponding to the study treatment actually received.

The following analysis approaches will be used:

All safety endpoints except hypoglycemia will be summarized regardless of the initiation of rescue or intensification therapy. This approach is referred to as the "including rescue" approach (IR). The Treatment Period will include all data from randomization up to 14 days after the last dose of study treatment for AEs, Tanner Staging and abdominal ultrasounds, up to 2 days after the last dose of study treatment for laboratory endpoints, and up to 5 days after the last dose for growth velocity and vital signs with the exception of analyses of Phase A alone, for which the additional follow-up days will not be included for participants who continue into Phase B (ie, Phase B data will be excluded from analyses of Phase A only).

SAEs and deaths will also be summarized inclusive of all post-randomization follow-up (APRFU), regardless of study treatment adherence and without an upper day limit.

AE summary measures will be tabulated by ertugliflozin dose in the subset of participants who were re-randomized at Visit 5/Week 12.

Hypoglycemia endpoints will be summarized excluding data collected following the initiation of rescue therapy or intensification therapy. This approach is referred to as the "excluding rescue" approach (ER).

Table 8 summarizes the analysis strategy by study phase and analysis approach.

Phase	Analysis Approach	Endpoints
Phase A	Treatment period, IR	all AE endpoints and PDLCs
Thase A	Treatment period, ER	hypoglycemia endpoints
A + B	Treatment period, IR	all safety endpoints except for hypoglycemia endpoints
	Treatment period, ER	hypoglycemia endpoints
	Treatment period + APRFU, IR	SAEs and deaths

Table 8 Analysis Strategy for Safety Endpoints by Study Phase

AE = adverse event; APRFU = all post-randomization follow-up; ER = excluding data after initiation of glycemic rescue/intensification therapy; IR = including data after initiation of glycemic rescue/intensification therapy; PDLC = predefined limits of change; SAE = serious adverse event(s).

The analysis of safety results will follow a tiered approach (Table 9). The tiers differ with respect to the analyses that will be performed. Adverse events (specific terms as well as system organ class terms) are either prespecified as "Tier 1" endpoints or will be classified as belonging to "Tier 2" or "Tier 3" based on the number of events observed.

Tier 1 Events

Safety parameters or AEs of special interest that are identified a priori constitute "Tier 1" safety endpoints that will be tested for statistical significance with p-values and 95% CIs to be provided for between-treatment differences in the proportion of participants with events; these analyses will be performed using the M&N method [Miettinen, O. and Nurminen, M. 1985], an unconditional, asymptotic method. For this protocol, events of symptomatic hypoglycemia, and AEs associated with genital mycotic infection (gender specific), hypovolemia, and UTI are considered Tier 1 events. AEs associated with UTI, hypovolemia, and genital mycotic infection will be identified by Custom MedDRA queries (CMQ), which will be defined in the sSAP.

Tier 2 Events

Tier 2 parameters will be assessed via point estimates with 95% CIs provided for differences in the proportion of participants with events (also via the M&N method [Miettinen, O. and Nurminen, M. 1985]).

Membership in Tier 2 requires that at least 8 participants in the combined ertugliflozin group or 2 participants in the placebo group exhibit the event; all other adverse events and predefined limits of change will belong to Tier 3.

The thresholds of events were chosen because the 95% confidence interval for the between-group difference in percent incidence will always include zero when fewer participants per group, respectively, experience events and thus would add little to the interpretation of potentially meaningful differences. Because many 95% confidence intervals may be provided without adjustment for multiplicity, the confidence intervals should be regarded as a helpful descriptive measure to be used in review, not a formal method for assessing the statistical significance of the between-group differences in adverse events and safety parameters that meet predefined limits of change.

In addition to individual events that occur in at least 8 participants in the combined ertugliflozin group or 2 participants in the placebo group, the summary measures of AEs consisting of the proportion of participants with any AE, a drug-related AE, an SAE, an AE that is both drug-related and serious, and discontinuation due to an AE, will be considered Tier 2 endpoints.

Tier 3 Events

Safety endpoints that are not Tier 1 or 2 events are considered Tier 3 events. Only point estimates by treatment group are provided for Tier 3 safety parameters.

Continuous Safety Measures

For continuous measures such as changes from baseline in laboratory and vital signs, summary statistics for baseline, on-treatment, and change from baseline values will be provided by treatment group in table format. In addition, for continuous Tier 3 safety endpoints, graphical representations of mean \pm SE values over time may be provided for selected endpoints.

For safety endpoints, all analyses will be based on the observed data (ie, with no imputation of missing data). Table 9 summarizes the analysis strategy for safety endpoints.

95% CI for **Treatment Descriptive** Tier Safety Variable/Endpoint p-Value **Comparisons Statistics** Tier 1 AEs of genital mycotic infection (gender X X X specific) AEs of hypovolemia X X X X X X Events of symptomatic hypoglycemia X X AEs of UTI X Tier 2[†] Episodes of severe hypoglycemia X X X X Requiring medical assistance X X X X Not requiring medical assistance X Episodes of documented hypoglycemia X X AE summary measures X X X Specific AEs ‡ or PDLCs (incidence ≥ 8 participants in the combined ertugliflozin group or ≥ 2 participants in the placebo group) X Tier 3 Specific AEs[‡] or PDLCs (incidence <8 participants in combined ertugliflozin group or <2 participants in the placebo group) Additional hypoglycemia endpoints X Change from baseline results (labs [including X bone biomarkers], vital signs, and abdominal ultrasounds) X Growth velocity and Tanner Staging

Table 9 Analysis Strategy for Safety

AE = adverse event; CI = confidence interval; PDLC = predefined limits of change; UTI = urinary tract infection; X = results will be provided.

Analysis of Hypoglycemia

For the hypoglycemia endpoints described in Section 9.4.2, the analyses of hypoglycemia will be performed separately for participants on a background of insulin and for participants not on a background of insulin at screening. Analyses of hypoglycemia combining participants on and not on a background of insulin are not planned.

[†] Endpoints listed here will qualify for Tier 2 only if the incidence is ≥8 participants in the combined ertugliflozin group or ≥2 participants in the placebo group.

[‡] Includes only those endpoints not prespecified as Tier 1 or not already prespecified as Tier 2 endpoints.

Tier 1 endpoints for hypoglycemia are the percentages of participants experiencing 1 or more episodes of symptomatic hypoglycemia.

Tier 2 endpoints for hypoglycemia are the percentages of participants experiencing 1 or more episodes of documented or severe hypoglycemia defined above. Summaries will be provided for all episodes.

Tier 3 endpoints for hypoglycemia are the percentages of participants with documented hypoglycemia as defined above:

- by lowest reported glucose category (<54 mg/dL [3.0 mmol/L], ≤70 mg/dL [3.9 mmol/L]); and
- by number of episodes.

Glucose categorization will be performed based on the units (mg/dL or mmol/L) in which the glucose measurements were reported. A participant's lowest glucose category will be classified as unknown only if no glucose measurements are available for that participant.

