8.3.4 Abdominal Ultrasound

Abdominal ultrasounds will be performed at the visits indicated in the SoA. The abdominal baseline ultrasound is to be performed at Visit 2/Week -1 or between Visit 2/Week -1 and Visit 3/Day 1/Randomization. The abdominal baseline ultrasound must be successfully submitted to and pass a quality check by the central imaging vendor *before* Visit 3/Day 1/Randomization. If necessary, the placebo run-in period can be extended by a week to ensure an acceptable abdominal ultrasound is on file before Visit 3/Day 1/Randomization.

If the **Visit 8/Week 54** or **Discontinuation Visit** abdominal ultrasound does not pass quality check, an acceptable abdominal ultrasound must be submitted within 2 weeks.

An independent reviewer will assess all ultrasounds for nephrocalcinosis.

If Discontinuation Visit procedures are not performed for a participant due to a site visit within 4 weeks (Section 8.1.9), an abdominal ultrasound will be performed if it was not performed at the site visit.

All ultrasounds will also be read locally to assess for any clinically relevant abnormalities. If any clinically relevant abnormality is detected, the site will be informed, and the participant will be followed up by the physician; the abnormality may be reported as an AE.

Abdominal ultrasound will be performed on all participants and images will be submitted to a central imaging vendor. The central imaging vendor will conduct a blinded independent central review (BICR). The BICR will not be done in real time. Details will be provided in the site imaging manual.

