8.10.8 Discontinuation Visit

The Sponsor should be contacted when a participant discontinues study medication, withdraws from the study, or interrupts study medication because of an AE or a laboratory safety test abnormality. All participants will be followed up until resolution (ie, return to normal or participant's baseline, diagnosis determined, or course of abnormalities established) for any laboratory safety test abnormality resulting in discontinuation.

All participants who discontinue study medication prior to completion of the protocolspecified treatment period will be encouraged to continue their participation in the study off study medication and be followed for all remaining study visits as outlined in the SoA.

PRODUCT: MK-8835

PROTOCOL/AMENDMENT NO.: 059-04

At a **Discontinuation Visit**, all laboratory testing will be performed after an overnight fast ≥10 hours in duration and all procedures outlined in the SoA are to be completed. **Discontinuation Visit** procedures will be performed on participants who discontinue study medication or discontinue the study as soon as possible after discontinuing study medication (within 4 weeks).

If a participant discontinues study medication before **Visit 5/Week 12**, the second randomization (and related assessments) should *not* be performed.

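### A protocol-compliant Discontinuation Visit ultrasound, or its repeat, can fall after the 14-day analysis window and so enter no planned summary

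*Combined protocol and SAP*

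**What the plan says.** Section 9.6.2 defines how long after the last dose a safety observation still belongs to the Treatment Period. For abdominal ultrasound the limit is "14 days after the last dose of study treatment for AEs, Tanner Staging and abdominal ultrasounds". For growth it is "up to 5 days after the last dose for growth velocity and vital signs", and for laboratory tests "up to 2 days after the last dose of study treatment for laboratory endpoints". SAEs and deaths are also summarized over all post-randomization follow-up with no day limit. Table 8 gives that second analysis to no other endpoint: over Phases A and B, every other non-hypoglycemia safety endpoint has the treatment-period analysis only. Sections 9.5.2 and 9.6.2 use observed safety data without imputation.

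The visit rules run on a longer clock. Section 8.10.8 asks for the Discontinuation Visit procedures "as soon as possible after discontinuing study medication (within 4 weeks", so 4 weeks is the outer limit. Section 8.3.4 places an ultrasound at Visit 8 and at the Discontinuation Visit. It also requires a scan when the other discontinuation procedures are waived because of a recent site visit that did not include one. If the Visit 8 or Discontinuation Visit scan fails its quality check, "an acceptable abdominal ultrasound must be submitted within 2 weeks". The readable text names scans at baseline, Week 54 and discontinuation only.

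**The concern.** The analysis window and the visit schedule have not been reconciled. A site can follow Sections 8.10.8 and 8.3.4 to the letter and produce a scan that Section 9.6.2 leaves out.

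The people exposed are chiefly those who stopped study drug, some of them because of adverse events. If such a participant stays in the study, as Section 7.1 intends, a later Visit 8 scan taken off drug is also outside 14 days unless drug stopped shortly before Week 54. A participant could then be scanned after baseline and contribute nothing to the nephrocalcinosis summary, which would rest mainly on those who tolerated treatment to the end.

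Section 4.2.1.2 names nephrocalcinosis, growth and development among the safety evaluations, and Section 7.1 says that certain data after discontinuation may matter and must be collected. The ultrasounds are collected, but the analysis has no stated place for the late ones.

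**Working it through.** The plan states no figure to reproduce here. The check puts the windows and the visit rules on one clock, days since last dose, and treats the day of stopping medication as the last-dose day.

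**Inputs**
- Ultrasound and Tanner window: 14 days (Section 9.6.2).
- Growth velocity window: 5 days (Section 9.6.2).
- Latest Discontinuation Visit: 4 weeks = 28 days (Section 8.10.8).
- Replacement scan: 2 weeks = 14 days (Section 8.3.4).
- No study drug on the morning of a site visit, so the last dose is normally at least 1 day before it (Section 8.1.8.1).
- Off study medication by Week 24: about 3.9%; planned sample 165, 110 on ertugliflozin and 55 on placebo (Section 9.9).

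**Discontinuation Visit scan.** Permitted through day 28, counted through day 14. Days 15 to 28 are compliant but excluded: 28 − 14 = 14 of 28 permitted days (50%). This is a share of calendar days, not a predicted share of visits.

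**Replacement scan.** The latest day is 28 + 14 = 42, which is 42 − 14 = 28 days past the window. This takes the 2 weeks from the visit (Section 8.3.4 does not say when they start) and the scan date as the submission date. The scan itself would be somewhat earlier, so day 42 is an outer limit.

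**Completer with a failed Visit 8 scan.** With the last dose 1 day before the visit, a replacement at 2 weeks falls on day 1 + 14 = 15, one day outside. On that reading, only a scan on the last permitted day misses.

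**Growth velocity, if measured at the Discontinuation Visit.** 28 − 5 = 23 of 28 permitted days (82%) are outside.

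**Scale.** By Week 24, 0.039 × 165 = 6.4 participants are expected to stop: 0.039 × 110 = 4.3 on ertugliflozin and 0.039 × 55 = 2.1 on placebo. No Week 54 rate is given. The 14% in Section 9.9 also counts censoring at rescue, so it is not a discontinuation rate. Assuming 5% to 15% stop ertugliflozin by Week 54, 110 × 0.05 = 5.5 to 110 × 0.15 = 16.5, or about 6 to 16 people. That is a ceiling, since it treats every stopper's scan as late.

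**Precision at that ceiling.** With zero cases, the one-sided 95% upper bound is 1 − 0.05^(1/n):
- n = 110: 2.69%
- n = 110 − 6 = 104: 2.84%
- n = 110 − 16 = 94: 3.14%

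**The case against.** An on-treatment window is a legitimate choice, and the amendment summary shows that post-dose limits for Tanner staging, growth velocity and vital signs were added on purpose, with the rationale redacted. Growth velocity is a rate, so adding time off drug dilutes it. Participants followed off drug may be taking other antihyperglycemic agents. These points stand, and they argue for keeping the on-treatment windows for Tanner staging and growth velocity. They do not explain why an on-time ultrasound should have no place in any summary.

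Several stronger inferences are tempting, but the documents do not support them:
- *The 2-week repeat allowance is itself longer than the window.* It equals 14 days. The gap arises because the window runs from the last dose and the repeat follows a visit that comes later. For completers the effect is about a day at most if the 2 weeks run from Visit 8.
- *Some 6 to 16 participants will lose a scan.* The rate is assumed, and the visit is meant to happen promptly, so many scans should fall inside 14 days.
- *Final height and Tanner stage are also lost.* The relevant rows of the Schedule of Activities are redacted, so it cannot be seen whether either is measured at the Discontinuation Visit.
- *The primary safety objective is undermined.* Its endpoints are adverse events and discontinuation because of them. Ultrasound, Tanner staging and growth velocity are Tier 3, with descriptive statistics only (Table 9).
- *The finding disappears altogether.* Scans are also read locally, a clinically relevant abnormality may be reported as an AE, a serious one enters the unlimited SAE summary, and Section 8.4.8 plans narratives for renal-related events and nephrolithiasis. These routes are partial: non-serious AEs share the 14-day limit, and the blinded central review is not done in real time.

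**Conclusion.** The mismatch holds for abdominal ultrasound. A compliant scan on days 15 to 42 after the last dose is outside the only planned summary, and for an early stopper it may be the only post-baseline nephrocalcinosis reading. The same gap may apply to Tanner staging (14 days) and growth velocity (5 days), on the condition that they are measured at the Discontinuation Visit.

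The number affected cannot be fixed from the documents. Even at the assumed ceiling the zero-event bound moves only from 2.7% to 3.1%, so precision is not the issue. What matters is that the loss is selective, falling on those who stopped drug, in a descriptive pediatric safety endpoint whose data are already collected. Whether visits after adverse events would run late is not known. The conclusion rests on the current wording of Sections 8.3.4, 8.10.8 and 9.6.2 and Table 8, and on finding no rule elsewhere that retains a late scan.

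**What to change.** In Section 9.6.2 and Table 8:

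1. Count the end-of-treatment ultrasound (Discontinuation Visit for early stoppers, Visit 8 for those completing on drug) and any replacement under Section 8.3.4 in the ultrasound summary whatever the day, with days since last dose shown.
2. Keep the existing on-treatment windows for Tanner staging and growth velocity.
3. Add ultrasound, Tanner staging and growth velocity to the *Treatment period + APRFU* row of Table 8 as a supplementary summary that includes later off-drug visits. Putting those visits here keeps readings many months off drug out of the on-treatment results.

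The change needs analysis-plan wording and one extra descriptive table. It calls for no new data, does not touch efficacy or alpha, and does not alter participant care. The downside is that a few scans in the ultrasound summary will have been taken some weeks off drug, which the days-since-last-dose display makes visible. It should be settled before unblinding.
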